**Figure 1: Experimental design**

The primary study aim is to improve patient satisfaction, education, and patient reported outcome measures after urethroplasty. All enrolled patients will complete a urethroplasty specific PROM survey, the Urethral Stricture Specific PROM (USS-PROM), as well as the Patient-Reported Outcomes Measurement Information System 29-item profile (PROMIS-29 v2.0) preoperatively, two weeks after catheter removal, and again at three months after surgery. Three months after surgery patients will also complete a decision regret scale. Patients in the control arm will receive surveys at the specified timepoint via RedCap. No additional visits will be required. Patients enrolled with the application will complete an overall assessment of GetWell Loop at the end of the study. This is administered in the application.

The second aim of the study is to decrease patient phone calls and messages due to improved patient education and troubleshooting provided by the interactive guide. Prospective chart review will be conducted on all patients enrolled in the study to evaluate the number of MyChart messages and phone calls.

The final aim is to decrease emergency department visits and improve postoperative outcomes. Postoperative complications will be rated on the Clavien-Dindo classification. Emergency department visits will be assessed by prospective chart review and patient interviews. Overall healthcare costs will be extrapolated based on the outcomes of emergency department visits.

DATA AND SPECIMEN BANKING

All data from GetWell Loop will be stored anonymously with unique patient identifiers in the GetWell Loop storage cloud, which can be downloaded remotely by the research team. Data will then be compiled and prospectively maintained in an encrypted

STU#:

REDCap database through our institution. Data will be accessible only to authorized members of the study team. Data will be kept indefinitely. For subjects agreeing to the future use of their data in institutionally approved studies not yet identified, data, either de-identified or identifiable, will be provided to future investigators as stipulated and approved in their IRB application and data security plan.

SHARING RESULTS WITH PARTICIPANTS

Results from the study and from the GetWell mobile health platform will be shared in person during the patient's follow-up at the completion of the study.

STUDY TIMELINES

The duration of the study is 12 months, however participation for each patient will be from time of their clinic visit where they sign up for urethroplasty and are recruited into the study to 90 days following their surgery. We plan to enroll 80 patients (40 per arm) and estimate this will take the entire year given our current clinical patient volume. We plan to start enrolling patients in August 2023 in anticipation of initiating launch of the application in August 2023. We anticipate completion of the participation in the study around July 2024.

INCLUSION AND EXCLUSION CRITERIA

Eligible patients include those over 18 years old who have a urethral stricture and are undergoing urethroplasty surgery with [name] at Northwestern Memorial Hospital. Exclusion criteria consists of patients without mobile phone capability to utilize GetWell Loop, physical or cognitive impairment precluding usage of a mobile phone or answering questionaries, and inability to consent to the study.

VULNERABLE POPULATIONS

PARTICIPANT POPULATION(S)

Accrual Number:	Category/Group: (Adults/Children Special/Vulnerable Populations)	Consented: Maximum Number to be Consented or Reviewed/Collected/Screened	Enrolled: Number to Complete the Study or Needed to Address the Research Question
Local	Adults	120	80
Study-wide		120	80
Total:		120	80

STU#:

RECRUITMENT METHODS

Patients scheduled to undergo urethroplasty surgery will initially be approached in clinic and given information regarding the study design and goals. All patients regardless of race/ethnicity/gender/socio-economic status will be approached. If patients have transportation issues and cannot make it to an in-person visit, a virtual visit can be offered instead, and patients can be recruit via this approach. If interested, the patient will then sign a generalized consent form enrolling them into the study. Eligible patients will then be randomized to one of two arms: standard care pathway and mHealth pathway. We will attempt to match patients based on demographics to have even distributions between the groups. We will utilize non-blinded block randomization technique due to the nature of the intervention pathway and need for continuous enrollment.

COMPENSATION FOR PARTICIPATION IN RESEARCH ACTIVITIES

To reduce attrition, financial incentive will be provided after completion of the 3-month follow up surveys with a \$100 Amazon gift card.

WITHDRAWAL OF PARTICIPANTS

Decision to participate is completely voluntary, and patients will be notified at the start of the study that if they choose not to participate, then they will continue with our standard care follow-up. Patients may drop out of the study or revert to the standard care pathway at any time.

RISKS TO PARTICIPANTS

Risks related to app use: GetWell's Privacy Policy is available on their website and attached with this protocol. Privacy and confidentiality risks include that while encryption is used for certain information using TLS (transport layer security), no method of transmission over the internet or electronic storage is 100% secure.

If the app does not work as intended or malfunctions, participants can contact the Customer Support [contact]). GetWell Network has a Chief Information Security Officer who oversees monitoring the app for potential security risks. One of the lead team members of this project will monitor and receive notifications from the secure messaging portal if there are any concerns on a weekly basis. Patients will also have the option to ask care-related concerns through Epic MyChart. All information in this study is kept confidential between the study team and the participants, and no third-parties will be involved. If the app fails to work as it should, there is no risk of medical harm to the patient. The app is to serve as a supplement to standard medical care. Patients will continue to receive medical recommendations at their initial medical appointments. If they choose to not answer the survey questions posed in GetWell, this will not affect their medical care. They have the option to skip any question if they are not comfortable answering.

POTENTIAL BENEFITS TO PARTICIPANTS

STU#:

Patients enrolled in our GetWell Loop application will have unique access to preoperative and postoperative educational materials, preoperative reminders, as well as postoperative trouble shooting pathways. We hope that implementation of this interactive mobile health platform will improve patient education, satisfaction, and outcomes after urethroplasty.

DATA MANAGEMENT AND CONFIDENTIALITY

Statistical outcomes will be analyzed based on intention-to-treat and per-protocol analysis. We will define statistical significance as p-value <0.05. With guidance from an institutional biostatistician, we will perform statistical analysis using R (R Foundation for Statistical Computing, Vienna, Austria) comparing all two study arms. After enrollment into the study, patients will be followed for a 90-day period. Data from the standard care pathway will be collected in person or during telehealth visits. All data from GetWell Loop will be stored anonymously with unique patient identifiers in the GetWell Loop storage cloud, which can be downloaded remotely by the research team. Data will then be compiled and prospectively maintained in an encrypted REDCap database through our institution. The confidentiality and privacy rights of all subjects enrolled in the study will be fully protected and HIPAA regulations will be strictly enforced. Data resulting from this study will not be linked to subjects. Subjects will not be referred to by name or initial in any publications.

PROVISIONS TO MONITOR THE DATA TO ENSURE THE SAFETY OF PARTICIPANTS

Only members of the research team and individuals who may have access to medical records and/or informed consent documents due to their job function at the participating sites may access the records.

PROVISIONS TO PROTECT THE PRIVACY INTERESTS OF PARTICIPANTS

No identifiable information about the patient, or provided by the patient, during the research, will be disclosed to, except:

- If necessary to protect subjects' rights or welfare (for example, if they are injured and need emergency care); or
- When the Collaborative Northwestern Institutional Review Board monitors the research or consent process; or
- When the Office for Human Research Protections (OHRP), the Office of Research Oversight (ORO), or other governmental regulatory agencies monitor the research; or if required by law.

The risk of the breach of confidentiality is possible in this study. However, all precautions will take place to make sure this issue is avoided. Data collected by study coordinators will be maintained in a secure server maintained by Northwestern University. The names of the patients will not be included on the primary database, but they will be followed by an ID number. When the results of the research are published or discussed in conferences, no information will be included that would reveal patients'

STU#:

identity. Patients who are uncomfortable or embarrassed to answer questions may choose to skip them or to discontinue their participation in the study at any time.

ECONOMIC BURDEN TO PARTICIPANTS

The mobile health platform involved in this research have no cost and will not be billed to the patient or their insurance.

CONSENT PROCESS

A two-stage consent process, which has been shown in a randomized trial involving patients undergoing prostate biopsies to reduce decisional anxiety and stress related to randomization to an experimental arm, will be utilized. Patients scheduled to undergo urethroplasty will initially be approached in clinic and given information regarding the study design and goals. If interested, the patient will have time to review the consent and have any questions answered, then sign a generalized consent form enrolling them into the study.

The process to document consent and re-consent in writing will be done as follows, per Good Clinical Practice guidelines:

The consent form will be signed and personally dated by the subject and by the person who conducted the consent prior to any study procedures. A signed copy of the consent form will be given to the subject and the original copy will be securely stored in the urology clinic. This process will be documented in the subject source documents.

NON-ENGLISH SPEAKING PARTICIPANTS

This study will provide access to participants with limited to no English proficiency and we will follow the IRB to effectively communicate the study to the participants during recruitment, consent and the duration of the study. This study will utilize the short form consenting process as described by the IRB. This short form consent will attest to the information in the informed consent and will be presented orally or by the participant's legal authorized representative. We will provide the short form to the participant or legal authorized representative. The short form will be signed and confirmation that the participant was consented in the language that is understandable by the participant, the person will be authorized by the IRB, there will be a witness to the presentation, the short form will be signed by the witness, the written summary will be signed by the witness and person obtaining consenting and finally a copy of the oral summary and short form will be given to the participant.

Once the participant is enrolled, we will adhere to the IRB standard requirements for non-English speaking participants and obtain certified translations of the documents related to the study.

PROTECTED HEALTH INFORMATION (PHI AND HIPAA)

This research study will involve the collection of Protected Health Information (PHI) from the patient's electronic medical record (EMR). PHI will also be created in this study: the

STU#:

questionnaires participants will be asked to complete will collect health information which may otherwise not be captured in the EMR.

HIPAA Authorization will be obtained from all participants. The following information may be collected for each participant:

- Name
- Medical Record Number
- Telephone number
- Email address

QUALIFICATIONS TO CONDUCT RESEARCH AND RESOURCES AVAILABLE

Persons involved in this study have experience with patient care and the handling of sensitive information. [name] is an assistant professor of urology here at Northwestern who specializes in reconstructive urology. Other staff, including residents, research coordinators, medical students, and nursing will have appropriate oversight by the PI. Staff are familiar with study sites at Northwestern Memorial Hospital / Northwestern Medical Group and Northwestern University culture. Facilities for conducting this research are adequate, including clinic space, secure computer workstations, and availability of access to other Northwestern University resources including the EDW. All persons assisting with research will be adequately informed regarding the protocol and research procedures and will have access to both text of the protocol and an “open-door policy” to promote a culture of questions, transparency, and communication.

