The purpose of the app is to guide patients through the perioperative period surrounding urethroplasty. The application will include preoperative reminders, informational videos, postoperative instructions, and an interactive guide for common postoperative concerns such as bladder spasms, wound healing, gross hematuria, and wound and catheter issues. We will be utilizing the survey data collected from the app to determine if PROMs improved with the convenience and accessibility of this app.

STU#:

The app is appropriately suited for adults 18 and older and is aesthetically easy to read/navigate and easy to understand.

App functionality:

GetWell Loop can be accessed via URL link (www.getwellnetwork.com) to their website using any computer with Internet capability. It can also be accessed in app format and can be downloaded onto iOS or Android devices via Google Play and Apple App Store. The app is free and there is no cost to the participant. Participants will use their own devices for the study. Participants without mobile phone/computer capability to utilize GetWell Loop will be excluded from the study. GetWell has technical support available on their website with Frequently Asked Questions as well as on demand technical support via a Customer Support [contact]) for any participants with app related technical issues. When a device's operating system is updated, the app's functionality will not be impacted. However, GetWell Loop's mobile app does require iOS 12.4 or later or Android 5.0+. The proposed care plan will last for 90 days and patients enrolled in the care plan will automatically be removed at the end of the study. When the study is over or when a participant withdraws, we will personally contact the participant to provide instructions on removal of the application.

Participant/user support:

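### The rating of GetWell Loop is collected only in the app at study end, with no stated route for patients who stop using it, so it is likely to overstate acceptability

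*Protocol*

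**What the plan says.** The Protocol places an overall assessment of the app under Aim 1 (Objectives). The text under Figure 1 in Procedures Involved fixes its timing and channel: "Patients enrolled with the application will complete an overall assessment of GetWell Loop at the end of the study. This is administered in the application". That same text names a survey route outside the app for the other arm only: "Patients in the control arm will receive surveys at the specified timepoint via RedCap".

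Withdrawal of Participants says: "Patients may drop out of the study or revert to the standard care pathway at any time". That sentence separates leaving the study from leaving the app pathway.

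The App functionality text describes what happens to the app itself. On withdrawal or at study end: "When the study is over or when a participant withdraws, we will personally contact the participant to provide instructions on removal of the application". On the 90-day care plan: "patients enrolled in the care plan will automatically be removed at the end of the study". On access without a phone: "GetWell Loop can be accessed via URL link".

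No section gives an expected reversion rate, and none describes how a patient who has stopped using the app would be asked to rate it.

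**The concern.** The questionnaire that measures opinion of the app sits inside the app. It is issued only once the period in which a dissatisfied patient may leave is over. Whether a rating is obtained then depends on continued use, and continued use plausibly depends on liking the app. The ratings that go missing would be those of the patients best placed to say what did not work.

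At stake is the acceptability figure for the mHealth arm. Such figures get quoted: the Protocol's own Background cites the share of users who found an earlier urology app easy to use. An analysis plan can define the denominator afterwards, but it cannot recover ratings that were never collected.

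**Working it through.** The Protocol states no figure for this rating, so there is nothing to reproduce. The check is a reading of the text, followed by a sensitivity calculation on assumed values.

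**Reading.** Time of rating: once, at study end. Channel: the application. Reversion: allowed at any time. Other channel for mHealth patients: none stated. REDCap: stated for control-arm surveys. Together these make the rating depend on the patient still being reachable through GetWell Loop when the study ends.

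**Inputs.** From the Protocol: 40 patients randomised to mHealth. Assumed: *d*, the share of the 40 who revert and do not rate; *p_s*, the favourable share among continuing users; *p_r*, the favourable share among reverters.

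**Formulas.**
- Reported share = *p_s*
- Share over the whole arm = (1 − *d*) × *p_s* + *d* × *p_r*
- Overstatement = *d* × (*p_s* − *p_r*)
- Worst-case bounds for the whole arm = (1 − *d*) × *p_s* to (1 − *d*) × *p_s* + *d*

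**Results with *p_s* = 90%.**

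| *d* | Patients of 40 | Whole arm (overstatement), *p_r* = 30% | Whole arm (overstatement), *p_r* = 60% | Worst-case bounds |
|---|---|---|---|---|
| 5% | 2 | 87% (3 points) | 88.5% (1.5) | 85.5% to 90.5% |
| 10% | 4 | 84% (6) | 87% (3) | 81% to 91% |
| 20% | 8 | 78% (12) | 84% (6) | 72% to 92% |
| 30% | 12 | 72% (18) | 81% (9) | 63% to 93% |

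Example: *d* = 20%, *p_r* = 30% gives 0.80 × 0.90 + 0.20 × 0.30 = 0.78, so the reported 90% is 12 points too high.

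If *p_r* = 90%, the overstatement is zero in every row. If reverters were the more satisfied group (*p_s* = 80%, *p_r* = 90%), the reported share would be too low by 0.5 points at *d* = 5% and by 3 points at *d* = 30%.

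**Against sampling error.** With 40 ratings and 90% favourable, the approximate 95% margin is 1.96 × √(0.90 × 0.10 / 40) = 0.093, or about 9 points. Six of the eight overstatements in the table lie within it. A confidence interval does not account for this kind of error, however, and more patients would not reduce it.

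**The case against.** A reader might infer that patients who revert are shut out of the assessment and that the rating is therefore certainly biased upward. The Protocol does not support that.

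- It nowhere says that reverters lose access or are not asked. The assessment is assigned to patients enrolled with the application, which can be read to include those who stopped using it.
- Automatic removal from the care plan comes only at study end, and the platform can be reached by web link. A reverter's account may still be open when the form is issued.
- The removal instructions concern withdrawal and study end, not reversion.
- Patients may revert for reasons other than dislike, so the direction is likely but not certain.

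All of this stands. It removes the certainty but not the gap. The website is the same platform, and nothing says that a reverter is asked to log back in. The gift card ("To reduce attrition, financial incentive will be provided after completion of the 3-month follow up surveys") is tied to the 3-month surveys and not expressly to the app assessment.

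It would also go too far to say that the trial cannot learn why patients left. The team personally contacts those who withdraw, and the Participant/user support text has the app monitored through patient feedback. That is not a structured rating, but it is a source of reasons.

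Finally, the rating has no control-arm counterpart and is not named in Study Endpoints. It does not enter the between-arm comparisons of the stricture PROM, PROMIS-29, decision regret, calls and messages, or emergency visits. This also stands, and it limits the severity.

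**Conclusion.** The concern holds in a limited form. As written, the rating may come mainly from continuing users, because one in-platform form at study end is the only stated way to obtain it. It is then likely to overstate acceptability among all 40 patients randomised to mHealth.

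The range of 1.5 to 18 points rests wholly on the assumed reversion rates and favourable shares, and on reverters not rating at all. The Protocol supplies none of these. No efficacy conclusion depends on the result. Minor severity.

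**What to change.** State in Procedures Involved that the app assessment will be sent at three months by REDCap link to every patient randomised to mHealth who remains in the study, including those who no longer use the app. Report the number rated out of all randomised to that arm, and show ratings for continuing users and reverters separately.

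A short form at the time of reversion may be added. It should be reported on its own, so that early and three-month ratings are not pooled.

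The cost is one extra REDCap form and a Protocol sentence, on a system the trial already uses for control-arm surveys. Some reverters will not respond, so the gap will narrow without closing, and the headline rating may be less favourable. Patients who leave the study altogether remain ordinary loss to follow-up and would not be recovered by this change.

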Participants will be trained to use the app during their initial in person visit if they choose to sign up for the study and are randomized to one of the mHealth arms. In addition, the app provides a tutorial for usage when first downloaded. Participants have access to GetWell's technical support Frequently Asked Questions on their website as well as on demand technical support via a Customer Support [contact]) for any participants with app related technical issues. The app will be monitored via patient feedback and data collection. Participants will be able to message providers with questions regarding the app or regarding their care through GetWell Loop and via Epic myChart. We will monitor survey data collected weekly to ensure that patients are able to complete surveys without issue.

Obtaining consent and the app's Terms of Service:

We will obtain written consent during a patient's initial urethroplasty appointment. Participants will not be consented via the app. The consent form is in-line with GetWell's Terms of Service, which are located on their website and uploaded along with this protocol. Data ownership is outlined in the Privacy Policy, which is also available on GetWell's website and attached with this protocol. All data collected and provided by participants is owned by GetWell. The Terms of Service will be summarized in the IRB consent form in a participant friendly manner. The Terms of Service are compliant with research regulations and local/state/federal law. We will plan to monitor for changes or updates to the Terms of Services by asking the GetWell developer team to email us when updates are made.

STU#:

Privacy and confidentiality protections:

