We will conduct a prospective, randomized controlled trial assessing the effectiveness of a mobile health application on perioperative outcomes and patient satisfaction for patients undergoing urethroplasty over a 12-month period. Experimental design including inclusion and exclusion criteria is outlined in **Figure 1**. Patients will undergo a two-stage consent process and a non-blinded randomization technique. Our institution performs 80-100 urethroplasty procedures a year. Our goal is to enroll 80 patients, 40 patients per arm. To reduce attrition, financial incentive will be provided after completion of the final study survey (obtained at three months postoperatively) with a \$100 Amazon gift card. If enrollment is significantly lower than expected, we will have continued institutional support and funding to extend our enrollment period. We will partner with GetWell Loop, an organization that has been well established within our hospital system, to develop a custom build for our application. We will evaluate our outcomes based on an intention-to-treat and per-protocol analysis and will define statistical significance as a p-value <0.05.

STU#:

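### Recruitment Methods sets an undefined attempt to match on demographics beside block randomisation; make it a named, pre-set stratification or remove it

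*Protocol*

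**What the plan says.** Three consecutive sentences in the Protocol, Recruitment Methods, govern allocation once the general consent form is signed.

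- The first assigns each eligible patient at random to standard care or to the app.
- The second adds a balancing step with no rule attached: "We will attempt to match patients based on demographics to have even distributions between the groups".
- The third names the method and gives its reason: "We will utilize non-blinded block randomization technique due to the nature of the intervention pathway and need for continuous enrollment".

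Procedures Involved repeats the description: "Patients will undergo a two-stage consent process and a non-blinded randomization technique". It also gives the size: "Our goal is to enroll 80 patients, 40 patients per arm".

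No readable section names a demographic variable, a stratum, a minimisation rule, the holder of the sequence, or whether upcoming assignments are hidden from recruiters. Figure 1, which outlines the design, is not reproduced in the copy read. The statistical analysis plan was not available.

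**The concern.** The problem is a rule that is present, not a detail that is absent. A block sequence fixes the next patient's arm. If matching also influences the arm, one of two things is true. Either the matching is built into the sequence in advance, which is stratification, or it acts outside the sequence and can override it. Calling it an attempt does not settle which.

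The setting makes the second possibility matter:

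- All patients have the same surgeon at one hospital (Inclusion and Exclusion Criteria).
- App patients are trained at the initial in-person visit (Participant/user support), so for patients recruited in person the arm is known in the clinic where recruitment happens.
- Most primary-aim measures are self-reported: the stricture questionnaire, PROMIS-29 and the decision regret scale.

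A patient placed by judgement could be placed for reasons linked to ease with an app or to expected recovery. The arms would then differ for reasons other than the app. This arises at enrolment, so an analysis plan cannot repair it.

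**Working it through.** The protocol gives no figure to reproduce here beyond 80 = 2 × 40, which is consistent. Three checks follow. Block sizes, trait frequencies and placement shares are assumptions, because the protocol states none of them.

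**1. Can the stated aim be met without judgement?**
Inputs: n = 80 in two arms (Procedures Involved); assumed permuted blocks of 4 and 6 in random order; a binary trait held by 50% or 30% of patients; 20,000 simulated trials per setting. The measure is the difference in trait percentage between arms.

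| Design | Gap ≥ 20 points | Gap ≥ 10 points | Arm sizes differ by ≥ 6 |
|---|---|---|---|
| Blocks, no strata, 50% trait | about 9% | not used | – |
| Blocks, no strata, 30% trait | about 6.5% | not used | – |
| Stratified by one factor | 0 of 20,000 | 0 of 20,000 | – |
| Stratified by two factors | 0 of 20,000 | at most 0.06% | about 1% |

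With 40 per arm, 20 points is 0.20 × 40 = 8 patients. An exact hypergeometric calculation (40 of 80 drawn, trait count fixed at 40 or 24) gives higher values, 11.7% and 8.7%. It fixes the trait count and ignores the blocks, so the simulated figures are the relevant ones for the blocked design that would remain if the matching sentence were deleted.

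**2. Why hide block sizes?**
If a recruiter sees past assignments and knows a fixed block size of 2m, the share of assignments certain in advance is 1/(m + 1). Blocks of 4 give 1/3 = 33% (about 27 of 80). Blocks of 6 give 1/4 = 25% (20 of 80). Enumerating all blocks gives the same values.

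**3. What would placement by judgement do? (illustration only)**
- Bias = share placed by judgement × SD difference between those placed in the two arms.
- Noncentrality = bias / √(2/40), in a t-test with 78 degrees of freedom at 0.05. The level is the protocol's; two-sidedness is assumed.
- Share 5% (4 patients), 0.5 SD: bias = 0.05 × 0.5 = 0.025 SD; noncentrality = 0.025 / 0.2236 = 0.112; false-positive rate 5.1%.
- Share 25% (20 patients), 0.5 SD: bias = 0.25 × 0.5 = 0.125 SD; noncentrality = 0.125 / 0.2236 = 0.559; false-positive rate 8.6%.
- At 0.25 SD the same shares give 5.0% and 5.9%; at 0.75 SD they give 5.3% and 13.2%.

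The documents give neither the share nor the SD difference, so this range says how harm would scale, not how large it is.

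**The case against.** The best defence is that this is only loose wording. The stated purpose is even distributions, and block randomisation is named in the next sentence, so stratified blocks are a natural reading; under them sequence and balance do not conflict. The text never says that staff choose arms. This largely stands. It limits the point to what the sentence allows and does not show that allocation will be non-random. It does not remove the point, because stratification is a rule set in advance and the protocol states no rule.

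A reader might go further and infer from *non-blinded* randomisation that the allocation list is open to recruiters. The document does not support that. The sentence gives its reason, the nature of the intervention pathway, which most naturally describes open-label treatment; continuous enrolment is a reason for using blocks. Unstated concealment is then an omission, and Figure 1 cannot be seen. Consent is also already placed before randomisation.

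A reader might also treat the false-positive range as the expected harm. It rests wholly on assumed inputs. At a 5% share it stays at 5.3% or below, and it reaches 8.6% or more only at a 25% share with a difference of 0.5 SD or more.

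**Conclusion.** The point holds in limited form, and the protocol should be amended. Recruitment Methods states a conduct rule that is not tied to the random sequence and, as written, allows assignment to depart from it. Whether any departure would occur is unknown, and no bias can be computed from the document. The gain from the change can be estimated: under assumed blocks of 4 and 6, stratifying takes the chance of a gap of 20 points or more in a stratified trait from about 9% (50% trait) or 6.5% (30% trait) to none seen in 20,000 trials. The sponsor's own aim is thus better served by a pre-set rule. The *non-blinded* wording calls for clarification only. Confidence is medium, because the benign reading is plausible.

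**What to change.** In Recruitment Methods, replace the matching sentence with: *Randomisation will be in permuted blocks stratified by [one or two named factors known at enrolment, for example age group]; no other matching will influence assignment.* Alternatively, delete it.

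State that the sequence is computer-generated, that block sizes are hidden from recruiters, and that each assignment is released through REDCap only after consent and eligibility are recorded. Adjust the analysis for the stratification factors; that line can sit in the analysis plan.

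As a wording clarification, describe the trial in Procedures Involved and Recruitment Methods as open-label with concealed allocation.

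**Cost.** A few hours to set up the randomisation in REDCap, which the trial already uses ("Patients in the control arm will receive surveys at the specified timepoint via RedCap"), plus the amended wording.

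**Downsides.** With two factors, arm sizes differ by 6 or more in about 1% of trials. Demographics that are not named are left to chance. If the sentence is deleted without stratification, all demographics are left to chance, with the 9% and 6.5% figures above.
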